WHO PS at time of recurrence/last follow-up	Dropdown list/checkbox 
 • 0 	Prompt entry if previous option (Postoperative WHO PS) is not 5

	
 • 1 • 2 • 3 • 4 	
SRS (SECTION/PAGE 7)		
Pre-radiation WHO PS	Dropdown list/check box 
 • 0 • 1 • 2 • 3 • 4 	Required entry. Allow one option only
Pre-radiation comorbidity	Check box 
 • Hypertension - systolic > 140 or diastolic > 90 and patients on medical treatment • Previous myocardial infarction • Congestive heart failure • Peripheral vascular disease • Previous stroke/TIA - If hemiplegia present, do not check • Hemi/paraplegia • Diabetes which requires medical treatment • Diabetes with end-organ damage - if so, do not check diabetes that requires treatment • COPD/Asthma • Renal disease • Mild liver disease - Hep B/C or cirrhosis without portal hypertension 	Required entry. Allow multiple options. Note to data collector: Age and comorbidities will be used to calculate the age adjusted Charlson comorbidity index. Each of these is defined in the guide provided

	
 • Moderate to severe liver disease - cirrhosis with portal hypertension, jaundice, ascites • Peptic ulcer disease • Cancer - excluding basal cell carcinoma • Metastatic cancer - if so, do not check cancer • Rheumatic or connective tissue disease • HIV/AIDS • Skin ulcers/cellulitis • Depression • Dementia • On Warfarin 	
Dose	Free field	Required entry
Early CTCAE toxicity (≤3 months)	Checkbox	Required entry
Toxicity	Free field	
Prompt entry if previous option (Early CTCAE toxicity (≤3 months)) is ticked
 
Note to data collector: https://ctep.cancer.gov/protocoldevelopment/electronic_applications/ctc.htm Use the following format: System class organ (SOC)-CTCAE term-grade e.g. nervous system disorders-headache-1. Select the complication with the highest toxicity grade

Late CTCAE toxicity	Checkbox	Required entry
Toxicity	Free field	
Prompt entry if previous option (Late CTCAE toxicity) is ticked
 
Note to data collector: https://ctep.cancer.gov/protocoldevelopment/electronic_applications/ctc.htm Use the following format: System class organ (SOC)-CTCAE term-grade e.g. nervous system disorders-headache-1. Select the complication with the highest toxicity grade

Meningioma progression/regrowth	Checkbox	Required
Scan date (at progression or last follow-up date if no progression)	DD/MM/YYYY	Required
WHO PS at time of progression/last follow-up	Dropdown list/checkbox 
 • 0 • 1 	Required. Allow one option only

	
 • 2 • 3 • 4 • 5 (dead) 	
fRT (SECTION/PAGE 8)		
Pre-radiation WHO PS	Dropdown list/check box 
 • 0 • 1 • 2 • 3 • 4 	Required entry
Pre-radiation comorbidity	Check box 
 • Myocardial infarction • Congestive heart failure • Peripheral vascular disease • Hemiplegia • Cerebrovascular disease • Pulmonary disease • Diabetes • Renal disease • Liver disease • Peptic ulcer disease • Cancer • Dementia • Connective tissue disease • AIDS • Hypertension • Skin ulcers/cellulitis • Depression • On Warfarin 	Required entry. Allow multiple options. Note to data collector: Age and comorbidities will be used to calculate the age adjusted Charlson comorbidity index. Each of these is defined in the guide provided
Number of fractions	Free field	Required entry
Fractionated dose	Free field	Required entry
Total dose	Free field	Required entry
Early CTCAE toxicity (≤3 months)	Checkbox	Required entry
Toxicity	Free field	Prompt entry if previous option (Early CTCAE toxicity (≤3 months)) is ticked

		Note to data collector: https://ctep.cancer.gov/protocoldevelopment/electronic_applications/ctc.htm Use the following format: System class organ (SOC)-CTCAE term-grade e.g. nervous system disorders-headache-1. Select the complication with the highest toxicity grade
Late CTCAE toxicity	Checkbox	Required entry
Toxicity	Free field	Prompt entry if previous option (Late CTCAE toxicity) is ticked Note to data collector: https://ctep.cancer.gov/protocoldevelopment/electronic_applications/ctc.htm Use the following format: System class organ (SOC)-CTCAE term-grade e.g. nervous system disorders-headache-1. Select the complication with the highest toxicity grade
Meningioma progression/regrowth	Checkbox	Required
Scan date (at progression or last follow-up date if no progression)	DD/MM/YYYY	Required
WHO PS at time of progression/last follow-up	Dropdown list/checkbox 
 • 0 • 1 • 2 • 3 • 4 • 5 (dead) 	Required. Allow one option only
Discharge from outpatient care/Lost to follow-up (SECTION/PAGE 9)		
Date of data entry into the database	DD/MM/YYYY	Required entry
Rescanned during the time between discharge/loss to FU and the date of data entry	Checkbox	Required entry
Date of scan	DD/MM/YYYY	Prompt entry if previous option (Readmitted/rescanned during the time between discharge/loss to FU and the date of data entry) has been checked
Reason?	Dropdown list: 
 • Seizure • Headache • Motor • Sensory • Language • Cognitive 	Prompt entry if previous option (Readmitted/rescanned during the time between discharge/loss to FU and the date of data entry) has been checked. Allow multiple options

	
 • Other 	
Peritumoural signal intensity on T2	Dropdown list/check box 
 • 0-5% • 6-33% • 34-66% • 67-100% • NA 	Prompt entry if previous option (Readmitted/rescanned during the time between discharge/loss to FU and the date of data entry) has been checked. Allow one option only Note to data collector: In relation to tumour volume. If only baseline CT available, NA
Peritumoural signal intensity on FLAIR	Dropdown list: 
 • 0-5% • 6-33% • 34-66% • 67-100% • NA 	Prompt entry if previous option (Readmitted/rescanned during the time between discharge/loss to FU and the date of data entry) has been checked. Allow one option only Note to data collector: In relation to tumour volume. If only baseline CT available, NA
Venous sinus nearby	Checkbox 
 • Superior sagittal sinus • Cavernous sinus • Sigmoid sinus • Transverse sinus • Confluence of sinuses 	Prompt entry if previous option (Readmitted/rescanned during the time between discharge/loss to FU and the date of data entry) has been checked Note to data collector: Tick box if within 10 mm, in direct contact or invading one of: superior sagittal sinus (SSS), sigmoid sinus (SS), transverse sinus (TS), cavernous sinus (CS) and the confluence of sinuses (CoS)
If yes, specify	Dropdown list/check box	Prompt entry if previous option (venous sinus nearby) has been ticked. Allow one option only
Separate, direct contact or invaded?	Dropdown list/check box 
 • Separate • Direct contact • Invaded 	Prompt entry if previous option (venous sinus nearby) has been ticked. Allow one option only
Major axis (mm)	Free field	Prompt entry if previous option (Readmitted/rescanned during the time between discharge/loss to FU and the date of data entry) has been checked Note to data collector: In mm to 1 dp. Measure on axial T1/CT + GAD
Minor axis (mm)	Free field	Prompt entry if previous option (Readmitted/rescanned during the time between discharge/loss to FU and the date of data entry) has been checked Note to data collector: In mm to 1 dp. Perpendicular to the major axis on axial T1/CT + GAD
Cor/sag major axis (mm)	Free field	Prompt entry if previous option (Readmitted/rescanned during the time between discharge/loss to FU and the date of data entry) has been checked Note to data collector: In mm to 1 dp. Maximum height
Verdict	Dropdown list/checkbox 
 • Related 	Prompt entry if previous option (Readmitted/rescanned during the time between discharge/loss to FU and the date of data entry) has been checked. Allow one option only

	
 • Unrelated 	Note to data collector: Were the symptoms attributed to the meningioma?
Outcome	Dropdown list/Checkbox 
 • Resume follow-up (active monitoring) • Surgery • SRS • fRT • Discharge • Lost to follow-up • Dead 	Prompt entry if previous option (Readmitted/rescanned during the time between discharge/loss to FU and the date of data entry) has been checked. Allow one option only Note to data collector: You will be directed to the relevant page/section dependent on the choice. If the patient died or was lost to follow-up after this interval scan, please choose one of the last two options, albeit the intention might have been to continue monitoring or intervene. If the option you choose is set to take place in the future, choose the option, save the data entered and exit the form with no further information required.
Overall outcome	Dropdown list/Checkbox: 
 • Dead • Alive 	Prompt entry if previous option (Rescanned during the time between discharge/loss to FU and the date of data entry) is not ticked. Allow one option only Note to data collector: You will be directed to section 10 if Dead is selected.
Mortality (SECTION/PAGE 10)		
Date of death	DD/MM/YYYY	Required entry
Cause of death	Dropdown list/checkbox 
 • Meningioma-related • Unrelated 	Required entry. Allow one option only Note to data collector: An example of a meningioma-related death would be for example status epilepticus in a patient who manifested seizures but didn't have treatment. An unrelated death would be for example a community acquired pneumonia. For the purpose of the study, any death occurring from a morbidity, which did not necessitate neurosurgical input/opinion will be classified as unrelated

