Two competing risk analyses will be performed. One assessing the cumulative incidence rate (CIR) of primary intervention at different time points following diagnosis stratified by PS and ACCI groups and the other will evaluate the CIR of disease progression. The competing event for the former will be non-meningioma-specific mortality either observed during follow-up or after being discharged from outpatient care. Patients who remain under follow-up will be censored at the last outpatient clinic appointment. Patients discharged alive from outpatient care will be censored at the last time they were seen by a healthcare physician up to the date of data entry.

For the disease progression analysis, mortality after hospital discharge could not be used as a competing event as the time interval between discharge and death could have seen radiological changes which meet the disease progression definition. Instead, four events will

be considered competing in nature, discharge from outpatient care, loss to follow-up, death during follow-up or an intervention before disease progression occurred with the first three grouped together. Censoring will only be done for patients who remain under follow-up at the last clinic appointment. To test the equality across CIR groups, the Fine and Gray test will be carried out. Plots of CIRs and 95% confidence intervals (CIs) will also be generated and compared to the training data set (11).

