3.10.3. Additional analyses

We envisage that imaging protocols in the participating centres are varied and non-standardised and thus, the growth rate for each meningioma will be determined using a joint longitudinal and event-time outcomes model which does not require regularly spaced time points, and adjusts for informative follow-up, assuming a different intercept and slope for each meningioma (25, 26). The sum of the regression coefficients of random and fixed effects for the slope estimated from the linear model will best represent the average growth rate for each meningioma. Absolute growth rate (AGR) will be defined as the increase in volume per year in cm³ whereas relative growth rate (RGR) will be defined as the percentage increase in volume per year.

Demographic differences across management and outcome groups will be explored with the χ^2 test for categorical variable and the Mann-Whitney U test or Student's t-test for continuous variables. Correlation between baseline variables will be evaluated using the Pearson correlation coefficient. Normally distributed continuous variables will be expressed as mean (standard deviation [SD]) whereas skewed variables as median (interquartile range [IQR]). Differences will be considered statistically significant at $P < 0.05$.

This statistical analysis plan will be reviewed prior to the final analysis of the study.

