If yes, which	Dropdown list/check box 
 • Internal carotid artery • Basilar artery • Vertebral artery • Middle cerebral artery • Anterior cerebral artery • Posterior cerebral artery • Optic apparatus (optic nerve and chiasm) • Trigeminal nerve • Facial nerve • Vestibulo-cochlear nerve • Other 	Prompt entry if previous option (In contact with critical neuro-vascular structures?) has been ticked
Major axis (mm)	Free field	Required entry Note to data collector: In mm to 1 dp. Measure on axial T1/CT + GAD
Minor axis (mm)	Free field	Required entry Note to data collector: In mm to 1 dp. Perpendicular to the major axis on axial T1/CT + GAD
Cor/sag major axis	Free field	Require entry Note to data collector: In mm to 1 dp. Maximum height
Location	Dropdown list/Check box 
 • Convexity 	Required entry. Allow one option only Note to data collector: as per ICOM classification (appendix 2)

	
 • Parasagittal • Parafalcine • Sphenoid wing • Anterior midline • Post fossa-midline • Post fossa-lateral & posterior • Tentorial • Intraventricular • Pineal region 	
Location subcategory	Dropdown list/Check box 
 • Anterior • Posterior • Falco-tentorial • Lateral • Medial (including ACP) • Cribriform plate/olfactory groove • Planum • Tuberculum/diaphragma sellae • Clival • Petro-clival • Anterior foramen magnum • Petrous • Squamous occipital • Posterior foramen magnum • Supratentorial • Infratentorial 	Required entry. Allow one option only Note to data collector: ICOM classification (appendix 2) Appropriate subcategories will appear based on main category selected
Side	Dropdown list/check box 
 • Right • Left • Midline 	Required entry. Allow one option only
MANAGEMENT DECISION (PAGE/SECTION 4)		
Decision	Dropdown list/Check box	Required entry. Allow one option only

	
 • Active monitoring • Surgery • SRS • fRT • Discharge from outpatient care • Lost to follow-up • Dead 	Note to data collector: You will be directed to the relevant page/section dependent on the choice. If the patient died or was lost to follow-up after this point in time, please choose one of the last two options, albeit the intention might have been to continue monitoring or intervene.
ACTIVE MONITORING (SECTION/PAGE 5)		
Scan date	DD/MM/YYYY	Required entry

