Outcome	Dropdown list/check box 
 • Resume follow-up (active monitoring) • Surgery • SRS • fRT • Discharge • Lost to follow-up • Dead 	Required entry. Allow one option only Note to data collector: You will be directed to the relevant page/section dependent on the choice. If the patient died or was lost to follow-up after this interval scan, please choose one of the last two options, albeit the intention might have been to continue monitoring or intervene. If the option you choose is set to take place in the future, choose the option, save the data entered and exit the form with no further information required.
SURGERY (SECTION/PAGE 6)		
Surgery date	DD/MM/YYYY	Required entry
Indication for intervention	Dropdown list/checkbox 
 • Clinical-radiological • Clinical • Radiological • Patient preference 	Required entry. Allow one option only
Preoperative WHO PS	Dropdown list/checkbox 
 • 0 • 1 	Required entry. Allow one option only

	
 • 2 • 3 • 4 	
Preoperative comorbidities	
Check box
 
 • Hypertension - systolic > 140 or diastolic > 90 and patients on medical treatment • Previous myocardial infarction • Congestive heart failure • Peripheral vascular disease • Previous stroke/TIA - If hemiplegia present, do not check • Hemi/paraplegia • Diabetes which requires medical treatment • Diabetes with end-organ damage - if so, do not check diabetes that requires treatment • COPD/Asthma • Renal disease • Mild liver disease - Hep B/C or cirrhosis without portal hypertension • Moderate to severe liver disease - cirrhosis with portal hypertension, jaundice, ascites • Peptic ulcer disease • Cancer - excluding basal cell carcinoma • Metastatic cancer - if so, do not check cancer 	
Required entry. Allow multiple options.
 
Note to data collector: Age and comorbidities will be used to calculate the age adjusted Charlson comorbidity index. Each of these is defined in the guide provided

	
 • Rheumatic or connective tissue disease • HIV/AIDS • Skin ulcers/cellulitis • Depression • Dementia • On Warfarin 	
Simpson grade	Dropdown list/check box 
 • 1-GTR • 2-GTR • 3-GTR • 4-STR • 5-STR 	Required entry. Allow one option only

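### The form's single decision field is overwritten by later death or loss to follow-up, so the management decision is not kept, and the open-ended note can also blur death after discharge

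*Protocol*

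**What the plan says.** Protocol section 3.8.3 lists the management strategies as active monitoring, surgery, SRS, fRT and discharge. It also says that the outcome of each clinic encounter will be recorded, from a similar list. Death and loss to follow-up are in neither list.

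The data form in Appendix 1 works differently. In form section 4 (Management decision), Lost to follow-up and Dead are added to the strategies in one field marked "Required entry. Allow one option only". The note to the data collector reads "If the patient died or was lost to follow-up after this point in time, please choose one of the last two options", and adds "albeit the intention might have been to continue monitoring or intervene". In form section 5 (Active monitoring), the Outcome field has the same structure and the parallel instruction "If the patient died or was lost to follow-up after this interval scan, please choose one of the last two options".

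Form section 9 serves patients who were discharged or lost. It asks whether the patient was "Rescanned during the time between discharge/loss to FU and the date of data entry". If there was no rescan, it asks Dead or Alive, with the note "You will be directed to section 10 if Dead is selected". Form section 10 (Mortality) records date and cause of death only.

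Section 3.10.1 bars death after discharge from the progression analysis: "mortality after hospital discharge could not be used as a competing event as the time interval between discharge and death" could have contained unseen radiological progression. Section 3.10.3 states: "Demographic differences across management and outcome groups will be explored".

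**The concern.** One field is asked to hold two facts: what was decided at the visit, and what happened to the patient afterwards. Where the two differ, the note says that the later fate wins.

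The first consequence follows directly from the text. A patient for whom monitoring or treatment was planned, but who died or was lost before the next recorded step, carries no record of that plan. The management groups are then defined partly by later survival and retention, and any comparison between them inherits that selection.

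The second consequence is a risk. The form section 4 note sets no limit on how much later the death may occur and does not exempt discharge. A site could apply it to a patient discharged at diagnosis who died years later, choose Dead, and go straight to the mortality page. Three things would be lost:

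- the check for rescans after discharge, and any progression seen on them;
- the correct end of observation for the Kaplan-Meier observed risk, which is the benchmark for calibration;
- the distinction between death during follow-up and death after discharge, which section 3.10.1 needs.

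**Working it through.** **1. Is the decision kept anywhere else?** Form section 4 allows one entry. Form sections 6 to 8 open only if an intervention is selected, section 9 only after discharge or loss, and section 10 only after death. None asks what had been decided at diagnosis. In form section 5 the earlier choice of monitoring survives, but the decision made at that scan (for example, to operate) is overwritten in the same way. The original decision is therefore unrecoverable for patients who die or are lost before the next step.

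**2. Which route does a discharged patient who later died take?**

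| Reading | Path | Rescan check | Death identifiable as after discharge |
|---|---|---|---|
| Discharge chosen | section 4 (or 5), then 9, then 10 | yes | yes |
| Note applied literally | section 4 (or 5), then 10 | no | no |

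The form section 5 wording does not close the gap, because any death after discharge also falls after the last scan. The mortality page cannot repair the second route, since it does not ask whether the patient was still under follow-up.

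**3. Which analyses are exposed?**

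- Validation (3.10.1) uses every patient, so nobody leaves the cohort.
- The intervention analysis counts unrelated death during follow-up and after discharge alike as the competing event.
- The progression analysis groups discharge, loss and death during follow-up, so recoding discharge as death stays inside one competing group.
- The Kaplan-Meier risk depends on the end date, which would move from discharge to death.
- The management-group comparisons in 3.10.3 use the coded decision.

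**4. Illustration of the Kaplan-Meier shift.** The only related figure in the Protocol is in section 3.4: 100 / 0.10 = 1000 patients, which reproduces. I borrow its 10% as a 10-year risk. The remaining inputs are assumptions: constant hazard, a share d discharged at year 1 and censored there, a share q of those dying evenly over years 1 to 10, no scans after discharge, and every such patient miscoded.

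Hazard: h = −ln(0.9)/10 = 0.010536, so 9h = 0.094824.

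After year 1 the miscoded patients sit in the risk set without being observed. Ignoring the small depletion by progression, the 10-year cumulative hazard is

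H = h + 9h × [(1 − d)/(dq)] × ln[1 + dq/(1 − d)], and risk = 1 − exp(−H).

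- d = 0.2, q = 0.2: H = 0.010536 + 0.094824 × 20 × ln(1.05) = 0.1031; risk 9.8%
- d = 0.2, q = 0.4: H = 0.010536 + 0.094824 × 10 × ln(1.10) = 0.1009; risk 9.6%
- d = 0.4, q = 0.2: H = 0.010536 + 0.094824 × 7.5 × ln(1.1333) = 0.0996; risk 9.5%
- d = 0.4, q = 0.4: H = 0.010536 + 0.094824 × 3.75 × ln(1.2667) = 0.0946; risk 9.0%

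With correct coding the risk is 10.0%. A simulation under the same assumptions gave 9.8%, 9.6%, 9.5% and 9.0%.

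**5. Cumulative incidence of progression.** With no other censoring this is (1 − d) × 0.10 + d × (1 − exp(−h)), where 1 − exp(−h) = 0.0105. For d = 0.2 it is 0.080 + 0.0021 = 8.2%. For d = 0.4 it is 0.060 + 0.0042 = 6.4%. Neither depends on whether the competing event is dated at discharge or at death.

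**The case against.** The note's own qualifier, "albeit the intention might have been to continue monitoring or intervene", names monitoring and intervention, not discharge. Discharge has its own option and its own page, which leads to the mortality page. Sections 3.8.3 and 3.8.4 separately require discharged patients' records to be searched for readmissions, rescans and deaths. Read without any limit, the note would also code as Dead someone monitored for eight years, which would empty the later pages for everyone who died. The workable meaning is death or loss before the next recorded step. Site training under section 3.9, including guides that are not shown, may say so.

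This stands as evidence of intent. A reader might infer from the note that discharged patients who later died necessarily become deaths under follow-up. The documents do not support that, because the form offers a proper route for them. What remains is that the wording sets neither the limit nor the exception, and a miscoded record could not be recognised from the form afterwards.

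A reader might also infer that early deaths drop out of the study or out of the performance-status and comorbidity strata. They do not. Baseline age, performance status and comorbidities are entered before the decision field, and the competing-risk analyses are stratified by those variables, not by management group.

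Finally, a patient who died before any repeat scan had no surveillance in practice. That is true, but it describes care received. It does not justify discarding the plan made at diagnosis, or discarding a planned intervention.

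**Conclusion.** The point holds in two parts of different strength. It is certain that the form discards the decision for patients meant for monitoring or intervention who died or were lost before the next recorded step. The management-group comparisons in section 3.10.3 are therefore conditioned on survival and retention. It is possible, but not certain, that discharged patients who later died are coded Dead, with loss of the rescan check, a shifted Kaplan-Meier end date and a blurred distinction that section 3.10.1 relies on.

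The effect on the primary validation is limited. In the illustration the 10-year Kaplan-Meier risk falls by about 0.2 to 1.0 percentage points from 10.0%, and that assumes every such patient is miscoded. It also assumes that discharge is the Kaplan-Meier censoring date, which the Protocol does not state. The cumulative incidence of progression is unchanged in the illustration, and would change little in practice unless progression on missed rescans matters. The Protocol gives no rates of discharge, early death or loss, so the number of patients affected is unknown. This should be corrected because a written coding rule causes it and the repair is cheap; it does not invalidate the design.

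**What to change.** In form sections 4 and 5, use two fields. The first records the decision made at that visit (active monitoring, surgery, SRS, fRT or discharge) and is never overwritten. The second records death or loss before the next recorded step, with its date.

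Replace the present notes with one that confines the second field to patients who have not been discharged. Route every discharged patient through form section 9, whether or not they later died. In section 3.10.3, define management groups from the first field at diagnosis.

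The cost is one extra dropdown with its date, revised branching in REDCap, an amended line in the data guide, and a re-check of records already entered. No new data source is needed, because sites already read the records that contain the decision.
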